## **9 ASSESSMENT OF SAFETY**

### **9.1 Safety Parameters**

Safety parameters for this study will include:

- Review of Systems
- Review of Adverse Events

- Laboratory Assessments: Concurrent with peripheral blood draws listed in the efficacy section and according to the study visit procedure chart, participants will provide blood samples for standard clinical safety testing. Safety panels will include:
  - CBC/Diff
  - PT/PTT
  - CPK
  - Total cholesterol
  - Albumin
  - Total Bilirubin
  - Conjugated Bilirubin
  - GGT
  - ALT/AST
  - Alkaline Phosphatase
  - Sodium
  - Potassium
  - CO2
  - Chloride
  - Calcium
  - BUN
  - Serum Creatinine
  - Serum Glucose
  - Serum Total Protein
  - Fasting lipid profile
  - BNP
- EKG
- Review of Medical History
- Review of Medical and Surgical Events
- Physical and Neurological Exam
- Review of Medication History
- Review of Current Medications and Therapies
- Review of any Adverse Events
- Collection of Vital Signs
- Collection of Height & Weight

## **9.2 Procedures for Reporting Adverse Events**

Adverse events must be recorded in the study source documentation and eCRFs. All events occurring after the informed consent is signed must be reported regardless of whether or not they are believed to be related to the study drugs or procedures. During study participation, adverse events should be followed by the study site principal investigator until resolved. All adverse events are graded according to the CTCAE.

## **9.3 Data and Safety Monitoring Board / Medical Monitor**

This study will not employ a Data and Safety Monitoring Board (DSMB) but adverse events will be reviewed by an appointed Medical Monitor who is otherwise not affiliated with the study.

In the event of a SAE, the Medical Monitor will be notified within 24 hours of notice of the event to the Coordinating Center, and details of the event will be provided for review at that time. Additional follow-up information will be provided to the Medical Monitor within 15 days of the initial event. Summaries of all other reported adverse events will be reviewed by the Medical Monitor on a quarterly basis.

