## 1.3 Study Design

This single center open-label pilot study will enroll 10 adults with genetically-confirmed Becker muscular dystrophy, who will receive the purified nutritional extract (-)-epicatechin 100mg/day orally for 8 weeks. After screening visits, participants will be enrolled in the study if they meet all inclusion criteria. They will be evaluated at baseline and at screening, day 1, and weeks 1, 2, 4 and 8. The main criterion for success of the study will be presence of one or more biologic or strength and performance outcome measures (Aims 1 and 2 below) that yield a response magnitude that allows for sufficient power in a Phase II B study with a sample size of 30 individuals.

Evaluations of efficacy will include:

- Assessment of peripheral blood creatine phosphokinase, follistatin, (-)-epicatechin pharmacokinetics, blood lactate during exercise, and baseline and post-treatment mRNA and miRNA biomarker profiles.
- Assessment of baseline and post-treatment muscle biopsy by histology, Western blot, immunostain and electron microscopy.
- Assessment of strength by isokinetic dynamometry and quantitative grip testing, exercise performance during a standardized recumbent cycle test, muscle perfusion of the quadriceps by NIRS during the exercise test, a 6-minute walk test, and body composition by dual-energy x-ray absorptiometry (DEXA).

Evaluations of safety will include comprehensive review of

- vital signs, height and weight
- medical history
- physical and neurological exam
- previous and concomitant medication history
- electrocardiogram
- laboratory safety panels for hematology and coagulation, standard blood chemistries (lipid, hepatic and metabolic profiles)

This is a greater than minimal risk study with prospect for direct benefit. A medical monitor will review safety-related evaluations throughout the duration of the study.

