### 7.3 Treatment Cycles Drug Dispensation

Medications will be dispensed for the entire period of time between study visits, and will be clearly marked as investigational drugs per UC Davis Investigational Drug Service Pharmacy procedures. The site will dispense study medication/placebo to the participant and will keep a medication log to document all study medication dispensed to participants. The participant will be instructed to take the study medication per protocol dosing schedule, every day during the eight-week treatment period.

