## **9.4 Duration of Participation / Follow-Up**

Participants will participate in the study for a period of approximately eight to ten weeks from the date of enrollment (eight weeks from start of study drug administration).

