## **9.5 Trial Stopping Rules or Discontinuation Criteria**

Participants may withdraw from the study at any time without prejudice. Study investigators may withdraw participants at any time for reasons such as:

- Inability to comply with study protocol
- SAEs
- Non-tolerable or non-manageable adverse events (AE)
- Severe or sustained unexplained laboratory abnormalities
- Recommendation of suspension of the study by the Medical Monitor

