## **10.8 Procedures for Minimizing Risks**

Confidentiality of medical information will be maintained throughout the study. Participants will be assigned identification numbers that will be used on all case report forms. No personally identifiable information will be released beyond the Study Coordinating Center without the participant's prior written consent. Data entered into electronic case report forms will be handled by the RedCap online CRF system and managed in compliance with FDA privacy and data retention standards for electronic clinical research data collection.

Safety data recorded during the conduct of this study will be transmitted directly to the Medical Monitor through the RedCap system. Data will be collected at each study visit and over the phone (family reported AEs) between study visits. Both AEs and SAEs will be reviewed by the Medical Monitor. AEs will be reviewed on a quarterly basis by the Medical Monitor.

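### The Medical Monitor's scheduled review of non-serious adverse events is quarterly, longer than the 8-week dosing period, so a participant can finish treatment before any scheduled independent review

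*Combined protocol and SAP*

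**What the plan says.** Section 9.3 dispenses with a DSMB and gives the independent safety role to one person, an "appointed Medical Monitor who is otherwise not affiliated with the study". Serious adverse events go to that person within 24 hours of notice to the Coordinating Center. For everything else, "Summaries of all other reported adverse events will be reviewed by the Medical Monitor on a quarterly basis". Section 10.8 says the same: "AEs will be reviewed on a quarterly basis by the Medical Monitor".

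Exposure is short. Under Section 7.3 the drug is taken "every day during the eight-week treatment period". Section 9.4 puts participation at about eight to ten weeks from enrolment, that is, "eight weeks from start of study drug administration".

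Three other statements bear on the point:

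- Section 1.3: "A medical monitor will review safety-related evaluations throughout the duration of the study". No frequency is attached.
- Section 10.8 also has safety data passing straight to the Monitor through RedCap, and Section 12.4 gives the Monitor read-only access to the whole dataset. Neither sets a time by which the data are to be looked at.
- Section 9.5 includes among the reasons for withdrawing participants "Recommendation of suspension of the study by the Medical Monitor".

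**The concern.** The only review interval stated for non-serious events is longer than the whole course of treatment. The plan can therefore be followed to the letter while a participant starts and finishes dosing without the independent reviewer having been scheduled to look at such events.

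This matters because of the events involved. Section 6.3.2 treats abnormal coagulation tests, rises in safety laboratory values and recurrent headache as important enough to trigger a dose reduction, yet none of them need be serious, so the 24-hour route may not pick them up. Section 10.7.1 lists bleeding as a potential risk and says that the compound's own effect on platelet aggregation and clotting times has not been reported. Section 8.1 has an open muscle biopsy at baseline and another at week 8. Section 7.1 states that safety is unproven in Becker patients. A modest shift seen in several participants is what an independent look across participants is for, and it is useful only if it takes place while people are still on drug.

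**Working it through.** The plan gives no figure of its own to reproduce. The check is timeline arithmetic.

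**Inputs**

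- Review interval Q: quarterly (9.3, 10.8), taken as 13 weeks, or 90 to 92 days.
- Dosing D: 8 weeks, or 56 days (7.3, 9.4).
- Participation P: up to 10 weeks, or 70 days (9.4).
- Sample size: 10 (6.1.1).

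**Assumptions.** The documents give no accrual rate and no start date for the quarterly clock. I assume reviews at fixed dates Q apart, start dates uniform within the cycle, and events uniform over dosing.

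**Step 1. Direct comparison.** 13 − 8 = 5 weeks: the interval exceeds dosing by 5 weeks (34 to 36 days). 13 − 10 = 3 weeks: it also exceeds the longest participation. This step needs no accrual assumption. It shows that dosing with no scheduled review is possible.

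**Step 2. Share of participants with no scheduled review while on drug.** (Q − D)/Q = 5/13 = 0.385, about 38%. In days, 34/90 = 0.378 and 36/92 = 0.391. Out of 10 participants that is an expected 3.8, so about six would have a review during dosing.

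**Step 3. The same over the longest participation.** (Q − P)/Q = 3/13 = 0.23.

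**Step 4. Mean wait from event to review.** Q/2 = 6.5 weeks (45 to 46 days), against 8 weeks of dosing: 6.5/8 = 0.81.

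**Step 5. Share of non-serious events first reviewed after that participant's dosing has ended.** An event at time t of dosing is reviewed before dosing ends with probability (D − t)/Q. Averaged over t this is D/(2Q) = 8/26 = 0.31, so 1 − 0.31 = 0.69 are reviewed afterwards.

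**Step 6. A shorter interval, for illustration.** For any Q below 8 weeks the share in Step 2 is zero for a full course. With Q = 4 weeks, two reviews fall within the 8 weeks and the mean wait is 4/2 = 2 weeks. Events in the first 4 weeks of dosing are always reviewed before it ends; those in the last 4 weeks are, on average, half the time. The share reviewed after dosing is therefore 0.5 × 0 + 0.5 × 0.5 = 0.25.

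**The case against.** The strongest reply is that the Monitor is not kept in the dark and that participants are not left unwatched. Safety data go directly to the Monitor (10.8), who can open the full dataset at any time (12.4). Table 3 has safety bloods and adverse event checks at weeks 2, 4 and 8, and the safety panel in 9.1 includes coagulation tests. Section 6.3.2 and Table 4 say what happens to an individual who meets the criteria, 9.2 has the principal investigator follow events to resolution, and 9.5 lets investigators withdraw people for laboratory abnormalities. All of this stands. It limits the concern to scheduled, independent, cross-participant review; none of these provisions sets such a review during exposure.

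The same facts rule out several stronger readings that a reader might infer:

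- *That events reach the Monitor only quarterly.* Sections 10.8 and 12.4 say otherwise. It is the review that is quarterly, not receipt of the data.
- *That Section 1.3 promises a review within each participant's exposure.* It gives no frequency, and quarterly review together with prompt notice of serious events could satisfy it. The wording should be aligned, but this is not a clear contradiction.
- *That the Monitor's recommendation is the only way to stop the study.* The list in 9.5 gives examples of reasons for withdrawing participants and is not exhaustive.
- *That the whole cohort would be treated before any review.* If the clock starts at first dose, this needs all ten to start within about 5 weeks of each other. The documents neither state nor exclude such accrual.

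**Conclusion.** The point holds as a gap in the timing of oversight. As written, 9.3 and 10.8 let a participant complete 8 weeks of dosing, and up to 10 weeks of participation, with no scheduled independent review of non-serious events, in a study that has no DSMB. That follows from the stated intervals alone.

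Its size depends on accrual, which the documents do not give. With uniform starts in a fixed 13-week cycle, about 38% of participants (38% to 39% using 90 to 92 days) have no scheduled review while on drug, and the mean wait is about 6.5 weeks. Other patterns would move these figures in either direction, so they are illustrative.

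The safeguards for serious events and for individual participants are real, so this is a cheap improvement and not a critical flaw. The documents do not support saying that the Monitor cannot see the data, or that nobody reviews it.

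**What to change.** In 9.3 and 10.8, replace the quarterly interval with a scheduled review at an interval shorter than the 8-week dosing period for as long as any participant is on drug. Every 4 weeks would serve as an illustration; the documents supply no basis for one particular value, and any interval below 8 weeks places at least one review within a full course. State that the review covers summaries of both adverse events and safety laboratory results across participants. Align the sentence in 1.3 with the chosen interval, and say in 10.8 how direct RedCap transmission relates to the scheduled review.

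The cost is a few additional short reviews of at most 10 participants, by a monitor already appointed, using data already collected and entered. No visit, test or treatment rule changes.

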## **9.4 Duration of Participation / Follow-Up**

Participants will participate in the study for a period of approximately eight to ten weeks from the date of enrollment (eight weeks from start of study drug administration).

## **9.5 Trial Stopping Rules or Discontinuation Criteria**

Participants may withdraw from the study at any time without prejudice. Study investigators may withdraw participants at any time for reasons such as:

- Inability to comply with study protocol
- SAEs
- Non-tolerable or non-manageable adverse events (AE)
- Severe or sustained unexplained laboratory abnormalities
- Recommendation of suspension of the study by the Medical Monitor

## 10 HUMAN PARTICIPANTS

### 10.1 Characteristics of the Study Population

Ambulatory male adults with a confirmed diagnosis of BMD, 18 years to 60 years, will be recruited.

#### Local Participant Population Available

The incidence of BMD is equal across racial and ethnic groups. It is assumed that the participant population of the study site should closely mirror the racial and ethnic distribution of the US population.

#### Projected Number of Participants Needed for this Study

	American Indian or Alaskan Native	Asian or Pacific Islander	Black, not of Hispanic Origin	Hispanic	White, not of Hispanic Origin	Other	Total
MALE	0	1	1	2	6	0	10

### 10.2 Participation of Children, Women and Minority Populations

BMD is an X-linked recessive disease affecting only males. However, female carriers of the disease can be symptomatic due to skewed X-inactivation. We have opted to study the most commonly affected population, males, to ensure patient homogeneity.

### 10.3 Sources of Research Material from Living Participants

Study data, blood and tissue samples collected will only be for research use or monitoring of study safety.

### 10.4 Recruitment of Participants

Participants will be recruited through the clinics of participating investigators, advertising and medical record screening in participating clinics. This trial will also be listed and updated on [www.clinicaltrials.gov](http://www.clinicaltrials.gov).

#### 10.4.1 Advertising

Any local advertising through newsletters or muscular dystrophy-associated organizations' mailings will be submitted to the local institutional review board (IRB) that provides overview of this project. An advertisement is included in Appendix C.

#### 10.4.2 Screening

Patients for this study will be identified through advertising, self-referral, referrals from other physicians and review of patients' clinic medical records currently under the care of the study site's principal investigator or co-investigators. Personnel who review existing patient medical records must be designated by the study site's principal investigator and must be an employee of that institution. A list of those personnel must be supplied to the institution's IRB. A telephone script (See Appendix B) will be used for the initial contact of potential study participants. If the potential participant is to be contacted by mail, the mailing letter template (Appendix B) should be used.

### 10.5 Informed Consent/Assent and Ethical Considerations

Informed consent/assent must be documented for each participant. The date and time of the consent/assent must be prior to the initiation of any study-related tests or procedures, including diagnostics that might be required to confirm a participant's study eligibility. The consent/assent form should supplement, not replace dialogue between the study principal investigator and the patient.

## 10.6 Retention of Participants

Care of each participant will be supervised by the participating site's principal investigator and study coordinator, who will schedule all visits and assessments.

If a participant is non-compliant, efforts will be made by site staff to ensure participant compliance, including participant/family teaching and increased frequency of phone contact to reiterate necessary information. If compliance does not improve, the investigator may decide to withdraw the participant from the trial. Any withdrawn participant will complete a follow-up visit along with an overview of systems and any adverse events that were noted during their study participation. Any ongoing adverse events will be monitored for 30 days after the participant's follow-up/withdrawal visit.

## 10.7 Potential Risks

### 10.7.1 Risks of Epicatechin

Animal and human safety studies suggest that (-)-epicatechin at doses of 1-2 mg/kg should be safe and well tolerated. In a study with green tea extracts containing (-)-epicatechin given orally to rats daily for 6 months, the no-observable-adverse-effect level (NOAEL) corresponded to 85 mg (-)-epicatechin/kg [67]. For the human dosing plan of 1 mg/kg, this provides a safety margin relative to the rat NOAEL of at least 85X. The dosing plan is also supported by published human studies, in which (-)-epicatechin doses of 1 and 2 mg/kg were administered with no adverse events were reported [11]. Potential risks based on the biological activities of (-)-epicatechin include:

**Hypotension** Given the reported effects of (-)-epicatechin on blood vessels, it is reasonable to assume that a potential risk may be associated with vasodilation. Of note is the fact that so far, no blood pressure reducing effects by (-)-epicatechin have been reported in normal subjects [81]. With cocoa based studies, blood pressure reducing effects are only reported in humans that have high blood pressure [81]. There is the possibility that patients undergoing pharmacologic treatment for high blood pressure if given (-)-epicatechin may develop hypotension through additive or synergistic effects.

**Migraines** The facilitation of migraines has been associated with the action of vasoactive substances [82]. The consumption of cocoa products has been reported to be associated with increased likelihood of migraine development [83, 84]. Thus, it is reasonable to surmise that (-)-epicatechin may increase the chances for migraine development in susceptible individuals.

**Bleeding** Anti-clotting like effects have been described for multiple members of the flavonoid family including (-)-epicatechin [85]. There is no report as to the effects that (-)-epicatechin per se may have on phenomena such as platelet aggregation or clotting times. There is a limited number of reports on the effects of cocoa on these endpoints. In general, they report effects on platelet aggregate. As with any compound, hypersensitivity reactions may occur, although no such reactions have been seen to date.

**Contraindications and Warnings** No contraindications are known. However, due to the possibility that (-)-epicatechin may interact with drugs with known antiplatelet effects to potentiate their activity, participants who are currently on long-term therapy with any such agents will be excluded from the study.

**Overdose** Neither the effects of overdose of (-)-epicatechin nor an antidote to overdose are known. The intraperitoneal (-)-epicatechin median lethal dose (LD50) reported for mice is 1000 mg/kg as stated in the MSDS provided by suppliers such as Sigma-Aldrich.

**Pregnancy and Lactation** In a developmental toxicity study in pregnant rats using a green tea extract, the no-observable-adverse-effect level (NOAEL) corresponded to 100 mg (-)-epicatechin/kg (the highest dose tested)[68]. No information is available on levels of (-)-epicatechin in breast milk. Risks of

### 10.7.2 Risks of Blood Tests

The risks of blood drawing include soreness or bruising at the site of the needle. A local numbing cream (EMLA) will be applied to the area. There are no side effects associated with the use of this cream. Rarely, a more serious injury, such as hematoma (bleeding under skin) or infection may develop.

### **10.7.3 Risks of Muscle Biopsy**

After the muscle biopsy patient may feel pain at the place of the biopsy. Patients usually find the pain easy to tolerate and that they rarely need to take a painkiller although Tylenol or ibuprofen is appropriate as needed for the next 24 hours. The muscle biopsy may leave a small scar and it is possible that the strength of that muscle might be slightly reduced in the short term.

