##### Participant Exclusion Criteria

- Currently enrolled in another treatment clinical trial.
- History of significant concomitant illness or significant impairment of renal or hepatic function.
- Use of regular daily aspirin or other medication with antiplatelet effects within 3 weeks of first dose of study medication.
- Regular participation in vigorous exercise.
- Symptomatic heart failure with cardiac ejection fraction <25%

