### 6.3.4 Concomitant Therapy

No new medications may be taken, except over the counter cold remedies, daily multivitamin, and Zantac, during the study period without the agreement of the Study Chair. The exception is any case where such medications are used to prevent injury or disability due to unforeseen adverse events.

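### Section 10.7.3 offers ibuprofen after each open muscle biopsy, around dosing with a drug that section 10.7.1 says may potentiate antiplatelet agents

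*Combined protocol and SAP*

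**What the plan says.** Section 10.7.3 (Risks of Muscle Biopsy) says that patients usually tolerate the pain well and "rarely need to take a painkiller although Tylenol or ibuprofen is appropriate as needed for the next 24 hours". The other effects it mentions are a small scar and a possible short-term loss of strength. It does not mention bleeding.

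Section 10.7.1 (Risks of Epicatechin) lists bleeding among the potential risks of the study drug: "Anti-clotting like effects have been described for multiple members of the flavonoid family including (-)-epicatechin". It also says how thin the evidence is: "There is no report as to the effects that (-)-epicatechin per se may have on phenomena such as platelet aggregation or clotting times". Under contraindications and warnings it says that "epicatechin may interact with drugs with known antiplatelet effects to potentiate their activity", and that for this reason "participants who are currently on long-term therapy with any such agents will be excluded from the study". The matching exclusion criterion in section 6.1.1 reads "Use of regular daily aspirin or other medication with antiplatelet effects within 3 weeks of first dose of study medication".

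Section 6.3.4 (Concomitant Therapy) bars new medications "except over the counter cold remedies, daily multivitamin, and Zantac, during the study period without the agreement of the Study Chair". Neither ibuprofen nor Tylenol is on that short list.

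**The concern.** The protocol treats potentiation of antiplatelet drugs as plausible enough to exclude people at entry. It then names a drug with that effect as suitable analgesia straight after an open surgical biopsy, around the time study drug is being taken. No section reconciles the two. At stake is a small, avoidable bleeding or hematoma risk at the biopsy site. There is also an operational problem: a coordinator who reads section 10.7.3 and then section 6.3.4 gets different answers on whether a participant may take ibuprofen, or even Tylenol, without asking the Study Chair. The point is one of participant safety and has no bearing on sample size, power or significance level.

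**Working it through.** The plan gives no figure to reproduce. The check compares sections and then counts opportunities for exposure.

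**Does the biopsy coincide with dosing?**
- Section 8.1 plans two open biopsies of the biceps, at baseline and after 8 weeks of treatment.
- Baseline: Table 3 puts the first biopsy and the first dispensing of epicatechin in the same Day 1 column. Section 8.1 schedules samples at 2 and 4 hours after a dose at baseline, so dosing starts at that visit. The overlap is clear.
- Week 8: section 8.1 also schedules post-dose samples at this visit, so at least one dose is taken at about the time of the second biopsy. The order of dose and biopsy is not stated, and Table 3 shows no dispensing at Week 8, so later doses cannot be assumed.

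**Does ibuprofen fall under the precaution?** Sections 10.7.1 and 6.1.1 refer to drugs with antiplatelet effects as a class, not only to aspirin. The documents do not say that ibuprofen belongs to it; that step is general pharmacology.

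**Does any other section settle the matter?**
- Section 6.3.4 does not. It omits both painkillers, so it disagrees with section 10.7.3. It also permits over-the-counter cold remedies without limiting those that contain aspirin or an NSAID. Its further exception covers unforeseen adverse events, and pain after a planned biopsy is not unforeseen.
- Section 6.3.3 stops study drug 2 to 5 days before surgery made necessary by a serious adverse event and restarts it 2 days afterwards. No reason is given, and no such pause applies to the planned biopsies.
- Section 6.3.2 makes abnormal PT/PTT a reason for dose reduction, so coagulation remains a concern during treatment and not only at entry.
- Section 10.7.2 names hematoma as a rare risk of a blood draw, while section 10.7.3 names none for an open biopsy.

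**How many opportunities?**
- Windows: 10 men (section 6.1.1) × 2 biopsies = 20 windows of 24 hours, at most.
- Doses per Day 1 window: 50 mg twice daily (section 6.3.1), so 24 h / 12 h = 2 doses, and 2 × 50 mg = 100 mg.
- Painkiller use, assumed at 5% to 20% of biopsies: 0.05 × 20 = 1 window; 0.20 × 20 = 4 windows.
- Counting only the 10 baseline windows: 0.05 × 10 = 0.5; 0.20 × 10 = 2.

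Ibuprofen's share of this use is unknown. With no bleeding rate in the documents, the calculation stops here.

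**The case against.** The strongest reply is that no rule is broken. The precaution is written for regular or long-term use, and a protocol may reasonably exclude chronic users of antiplatelet drugs while tolerating a day of as-needed analgesia. That is correct. What remains is a conflict with the reason for the precaution, which applies most directly at a fresh wound.

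It can also be said that the harm joins an unproven interaction to a property of ibuprofen that the documents never mention. Both parts are true. But the protocol acted on the bare possibility when it set its entry criteria, and the same caution should govern its own advice. The property of ibuprofen is basic knowledge of the drug class.

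The Week 8 overlap is weaker. Section 5.3.3 gives a plasma half-life of about 2.5 hours, section 1.1 says most of the drug and its metabolites have left plasma by 8 hours, and the order of dose and biopsy is not given. This stands as a limit, and the point rests mainly on the baseline biopsy.

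Finally, section 6.3.4 taken literally already puts ibuprofen behind the Study Chair's agreement, and the protocol has other safeguards: PT/PTT in the safety panel, dose reduction if these are abnormal, and a medical monitor. Section 6.3.4 would help if section 10.7.3 did not say the opposite. PT and PTT do not measure platelet function, so that cover is partial.

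**Conclusion.** The concern holds and is minor. The analgesic advice is inconsistent with the reasoning behind the antiplatelet precaution, and nothing in the protocol resolves it. The overlap with dosing is clear at baseline and probable but less certain at Week 8. The exposure is bounded by 20 windows, and actual use should be far lower because the protocol itself expects painkillers to be needed rarely. The range of 1 to 4 windows depends wholly on the assumed 5% to 20% use. The conclusion rests on one premise from outside the documents, ibuprofen's antiplatelet effect, and on taking the protocol's stated precaution at face value. It does not claim that epicatechin has been shown to increase bleeding.

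**What to change.** - In section 10.7.3, delete ibuprofen and name acetaminophen (Tylenol) as the analgesic after both biopsies.
- In section 6.3.4, add acetaminophen to the medications allowed without the Study Chair's agreement. Advise against products containing aspirin or an NSAID, cold remedies included, for 24 hours after each biopsy.

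The cost is one phrase in section 10.7.3 and one or two lines in section 6.3.4, with no new visit, test or procedure. The downside is a slightly narrower choice of painkiller. A participant who cannot take acetaminophen can still use the Study Chair route, and hepatic concerns are limited because the exclusion criteria already cover "History of significant concomitant illness or significant impairment of renal or hepatic function".
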